2.2 Background - Study Disease(s)

The proposed clinical trial is a phase 1b/2a, open-label, multicenter study of the administration of atezolizumab (MPDL3280A) in combination with NT-I7 in patients with anti-PD-1/PD-L1 naïve or relapsed/refractory high-risk skin cancers: cutaneous Squamous Cell Carcinoma (cSCC), Merkel Cell Carcinoma (MCC) and melanoma.

High risk melanoma, MCC and cSCC share many attributes. Biologically, as a group they have the highest mutational burdens from skin exposure to ultraviolet (UV) radiation and accordingly have amongst the highest response rates to inhibition with PD-1/PD-L1 blockade in the range of 30-40+% ORR. Unfortunately, PD-1/PD-L1 blockade fails to induce complete responses (CRs) in most patients.

Therapeutically, these are surgical diseases before dissemination and are usually treated by the same set of physicians (dermatologists, cutaneous surgical oncologists and cutaneous-based oncologists). Thus, clinical trials with all three diseases utilizing the same group disease and clinical trial experts are practical and can be efficient.

Investigational trials of checkpoint inhibitors in all 3 disease groups have shown similar ORR (see table below).

Tumor Type	Agent/Phase trial	ORR
cSCC	Cemiplimab (Phase II) Two advanced cSCC expansion cohorts (Phase I)	47% https://investor.regeneron.com/news-releases/news-release-details/fda-approves-libtaylor-cemiplimab-rwlc-first-and-only-treatment
MCC	Pembrolizumab (Phase II) Avelumab (Phase II)	33%-56% 5 6
Melanoma	Pembrolizumab (Phase III) Nivolumab (III)	33%-40% 7 8

Abbreviations: cSCC=cutaneous squamous cell carcinoma; MCC=Merkel cell carcinoma; ORR=objective response rate.

IL-7 is a homeostatic growth factor for T-cells that normally contributes to maintaining the normal number of peripheral blood T-cells. IL-7-mediated signaling can induce proliferation in the absence of T-cell receptor (TCR) signaling [9](#). IL-7 signals through the IL-7 receptor (IL-7R) heterodimer composed of the common γ -chain (CD132) cytokine receptor and a unique IL-7R α (CD127). During normal conditions, IL-7R expression is maintained on resting T-cells [10](#) and exogenous IL-7 induces expansion of most categories of T-cells.

In clinical studies IL-7 has been shown to have numerous characteristics that could provide synergism with anti-PD-L1:

1. Increase peripheral blood T-cells by several-fold with little toxicity [11-15](#),
2. Expand all categories of T-cells including CD8+, CD4+ and memory T-cells [12](#),
3. Increase the total body complement of T-cells including increased size of lymph nodes, spleen, liver [16](#),
4. Increase TCR diversity by preferentially stimulating the growth of T-cell receptor excision circles (TREC)-positive, naïve T-cells [16](#). Continuous signaling by IL-7 induces anti-apoptotic and co-stimulatory responses that are essential for the survival of naïve T-cells.
5. Increase tissue infiltration of T-cells into gut mucosa (other tissues including tumor have not been examined) [17](#).
6. Reverse neutrophil lymphocyte ratios [Cancer Immunotherapy Trials Network (CITN)12-03 (NCT01881867), manuscript submitted]
7. Augment immune-mediated control of both tumors and viruses [10](#).

Very few preclinical studies have combined IL-7 with PD-1 or PD-L1 checkpoint blockade and there have been no human trials for these combinations, in large part due to a lack of availability of long-acting rhIL-7. However, there is sufficient inferential data to support testing the combination in a clinical trial setting.

The current trial will test whether addition of NT-I7 (rhIL-7- hyFc), a long-acting IL-7, to atezolizumab, using a NT-I7 regimen known to increase the total body complement of T-cells, will increase the frequency and/or depth of clinical responses to atezolizumab monotherapy and, thereby, provide clinically meaningful outcomes for patients with anti-PD-1/PD-L1 naïve or relapsed/refractory high-risk melanoma, MCC and cSCC.

2.3 Agent(s)

2.3.1 Atezolizumab (MPDL3280A)

TECENTRIQ® (atezolizumab) is a humanized immunoglobulin G1 (IgG1) monoclonal antibody that is produced in Chinese hamster ovary (CHO) cells. Atezolizumab targets PD-L1 on tumor-infiltrating immune cells (ICs) or tumor cells (TCs) and prevents interaction with the PD-1 receptor and B7.1 (CD80), both of which function as inhibitory receptors expressed on T-cells and other immune cells. Interference of the PD-L1:PD-1 and PD-L1:B7.1 interactions may enhance the magnitude and quality of the tumor-specific T-cell response through increased T-cell priming, expansion and/or effector function. Atezolizumab was engineered to eliminate Fc-effector function via a single amino acid substitution at position 298 on the heavy chain, which results in a non-glycosylated antibody that has minimal binding to Fc receptors and, consequently, eliminates detectable Fc-effector function. By eliminating Fc-effector function and antibody-dependent T-cell-mediated cytotoxicity, antibody-mediated clearance of activated effector T-cells is also eliminated.

Expression of PD-L1 is prevalent among many human tumors [18](#), and its overexpression is associated with poor prognosis for patients with certain cancers [19-22](#). Therefore, interruption of the PD-L1/PD-1 pathway represents an attractive strategy to reinvigorate tumor-specific T-cell immunity.

Treatment with atezolizumab has shown anti-tumor activity in many tumor types, including lung cancer, bladder cancer, melanoma, renal cell carcinoma (RCC), colon cancer, ovarian cancer, gastric cancer, breast cancer, head and neck carcinoma, and hematologic malignancies. Atezolizumab has the potential to produce durable efficacy outcomes. Atezolizumab is being evaluated both as a single agent and in combination with other chemotherapies and targeted agents. Currently, pivotal studies are underway in non-small cell lung cancer (NSCLC), RCC, urothelial carcinoma (UC), prostate cancer, breast cancer, and various other tumors.

[REDACTED]

[REDACTED]

[REDACTED]

[REDACTED]

[REDACTED]

[REDACTED]

[REDACTED]

[REDACTED]

Refer to the Atezolizumab IB for additional details on the safety and efficacy of atezolizumab.

2.3.2 NT-I7 (rhIL-7-hyFc)

NT-I7 is being co-developed by NeoImmuneTech, Inc. and its partner Genexine, Inc. for use in the treatment of cancer patients and in conditions where lymphocyte number and/or function is suppressed. NT-I7 is a long-acting IL-7 cytokine consisting of human IL-7 and a hybrid crystallizable fragment (hyFc) region, which extends its half-life. The active ingredient is recombinant human interleukin-7 fused to a hybrid Fc region of a human antibody (rhIL-7-hyFc). HyFc[®] is composed of the human immunoglobulin D (IgD) hinge region fused to the N-terminal region of homologous constant region domain 2 (CH2) from IgD, which is in turn fused to the C terminal region of CH2 and the entire homologous constant region 3 (CH3) region of the antibody immunoglobulin G4 (IgG4). A detailed structural diagram of NT-I7 is shown in the NT-I7 IB.

In preclinical studies, NT-I7 has demonstrated potent anti-tumor efficacy, as well as an increase in peripheral T-cells and tumor infiltrating lymphocytes as a monotherapy, in combination with chemo/radiotherapy, and in combination with immune checkpoint inhibitors (CPIs).

Recombinant human IL-7 (rhIL-7), previously developed by Cytheris, was administered to over 390 subjects in clinical trials, including patients with chronic human immunodeficiency virus (HIV) or hepatitis C virus (HCV) infections, patients with refractory solid tumors, and patients after allogeneic stem cell transplantation [23](#). These combined clinical studies demonstrated proof

of mechanism for the use of exogeneous IL-7 in patients with regard to substantial increases in T-cell count, tolerability and overall safety profile. Cytheris' rhIL-7 therapeutic platform faced fundamental technical challenges, however, with a short half-life, lack of molecular stability due to an intrinsically unstable protein and poor production yield. NT-I7 overcomes the fundamental problems that stalled previous rhIL-7 programs by fusing the C-terminal of IL-7 to its proprietary hyFc long-acting platform.

[REDACTED]

Refer to the NT-I7 IB for additional details on the safety of NT-I7.

2.4 Overall Risk/Benefit and Ethical Assessment

T-cells play a pivotal role in inducing antigen-specific immune responses to attack cancer cells, as they can recognize cancer antigens, destroy cancer cells and differentiate into memory T-cells to facilitate long term immunity. The anti-tumor efficacy of T-cells can be enhanced by increasing the diversity of the T-cell receptor repertoire to enable recognition of specific antigens expressed by cancer cells, expanding T-cell clones responsive to tumor specific antigens and accelerating differentiation to memory T-cells to increase tumor tissue infiltration [27:28](#). Chemotherapy and radiotherapy are widely used as standard of care for the majority of cancer patients, but these can kill T-cells and compromise overall anti-cancer efficacy by suppressing bone marrow function and destroying immune cells in the blood [29:30](#).

T-cell lymphopenia in cancer patients is associated with lower clinical anti-tumor responses and lower survival rates. To date, IL-2 (Proleukin[®] [aldesleukin]) is the only Food and Drug Administration (FDA)-approved cytokine product available as a therapeutic option to induce the proliferation and activation of T-cells. However, the clinical application of IL-2 is very limited due to serious adverse effects such as capillary leak syndrome and compromised efficacy through the increased proliferation of regulatory T-cells that inhibit anti-tumor immune responses [31:32](#).

IL-7 is a crucial factor for the growth and activation of T-cells, and serves as a key player in the differentiation, proliferation and survival of naïve and memory T-cells. Importantly, it does not induce proliferation of regulatory T-cells. IL-7 is also referred to as a homeostatic cytokine, as IL-7 receptors (CD127) expressed on the surface of T-cells are downregulated or internalized if T-cells are overactivated by IL-7. To date, there have been no reports of rhIL-7 (CYT107 or CYT99007, Cytheris, Inc.) causing cytokine release syndrome, a serious immune-mediated adverse reaction caused by excessive immune activation associated with other cytokine therapeutics [11-16:33-44](#).

[REDACTED]

[REDACTED]

The protocol will administer NT-I7 via the IM route starting from 120 µg/kg, the dose that is only 1/4 of the dose currently being tested in the Phase 1b clinical study with solid tumor patients in Korea (480 µg/kg). The dose will be escalated up to 1200 µg/kg to find the MTD and/or the RP2D.

With no specific overlapping target organs toxicities identified in nonclinical or clinical studies in the individual single-agent toxicology studies for NT-I7 and atezolizumab, evidence suggests a very low potential for overlapping toxicity in patients treated with NT-I7 in combination with atezolizumab.

Taken together, data from non-clinical and clinical studies suggest that the addition of NT-I7 to atezolizumab, using an NT-I7 regimen known to increase the total body complement of T-cells, has the potential to increase the frequency and/or depth of clinical responses to atezolizumab monotherapy and, thereby, provide clinically meaningful outcomes for patients with anti-PD-1/PD-L1 naïve or relapsed/refractory high-risk melanoma, MCC and cSCC.

More detailed information about the known and expected benefits and risks and reasonably expected AEs of atezolizumab and NT-I7 may be found in the respective IBs.

The Sponsor (NeoImmuneTech), via the Immune Oncology Network (ION) Coordinating Center, will immediately notify the Principal Investigators (PIs) if any additional safety or toxicology information becomes available during the study.

This study will be performed in compliance with the protocol, International Council for Harmonisation (ICH) Good Clinical Practice (GCP) and applicable regulatory requirements. Aspects of the study concerned with the investigational medicinal product(s) (IMPs) will meet the requirements of European Union – Good Manufacturing Practice (EU GMP).

3. OBJECTIVES AND ENDPOINTS

This study will evaluate the safety and tolerability and assess the antitumor efficacy of NT-I7 in combination with atezolizumab (Phase 1b/2a) in patients with anti-PD-1/PD-L1 naïve or relapsed/refractory high-risk skin cancers (cSCC, MCC, melanoma). Specific objectives and corresponding endpoints for the study are outlined in Table 2.

Table 2 – Study Objectives and Endpoints

Objectives	Corresponding Endpoints
Primary Objective	

To evaluate the safety and tolerability of NT-I7 in combination with atezolizumab (Phase 1b), including estimation of the Maximum Tolerated Dose (MTD) and/or the Recommended Phase 2 Dose (RP2D)
 
Phase 2a: To evaluate the Objective Response Rate (ORR) according to RECIST v1.1 and iRECIST, as determined by the investigator
	
 - Incidence, nature, and severity of adverse events graded according to NCI CTCAE v5.0 - Incidence and nature of DLTs - Potential correlation with PK, pharmacodynamic, safety, and efficacy parameters - Objective Response Rate (ORR), defined as the percentage of patients who have at least one confirmed partial response (PR) or complete response (CR) according to RECIST v1.1 and iRECIST, as determined by the investigator
Secondary Objectives	

To evaluate immunogenicity of NT-I7 in combination with atezolizumab
 
To make a preliminary assessment of the anti-tumor activity of NT-I7 in combination with atezolizumab
	
 - Incidence of anti-drug antibody (ADA) to NT-I7 during the study relative to the prevalence of ADA at baseline - Disease Control Rate (DCR), defined as proportion of patients with a best overall response of CR, PR or stable disease (SD). - Duration of objective response (DOR), defined as the time from the first occurrence of a documented objective response to the time of the first documented disease progression or death from any cause, whichever occurs first, per RECIST v1.1 and iRECIST as determined by the investigator - Progression Free Survival (PFS), defined as the time from the first study treatment (Cycle 1, Day 1) to the first occurrence of progression or death from any cause, whichever occurs first, per RECIST v1.1 and iRECIST as determined by the investigator - Overall survival (OS), defined as the time from first study treatment (Cycle 1, Day 1) to death from any cause
Exploratory Objectives	

To make a preliminary assessment of PK parameters of NT-I7 in combination with atezolizumab
	
The endpoints will include the evaluation of the effect of the investigational treatment combination on the tumor microenvironment, based upon

Objectives	Corresponding Endpoints

To make a preliminary assessment of biomarkers that might act as pharmacodynamic indicators of activity of NT-I7 in combination with atezolizumab
 
To make a preliminary assessment of biomarkers that might act as predictors of anti-tumor activity of NT-I7 in combination with atezolizumab
	
baseline and post-baseline tumor biopsy comparisons of:
 
 - Serum concentration of NT-I7 administered in combination with atezolizumab at specified timepoints for the following parameters: Area under the concentration time-curve (AUC) Maximum serum concentration (C_{max}) Minimum serum concentration (C_{min}) Clearance (CL) - Number, distribution, and phenotype of tumor-infiltrating cells - PD-L1 expression - Expression of Interferon γ (IFNγ) and associated inflammatory gene expression in the tumor microenvironment - Changes in tumor microenvironment that correlate with response or provide information on potential actionable causes for lack of clinical benefit

Abbreviations: ADA=anti-drug antibodies; AUC=area under the curve; CL=clearance; C_{max}=maximum serum concentration; C_{min}=minimum serum concentration; CR=complete response; CTCAE=Common Terminology Criteria for Adverse Events; DCR=disease control rate; DLT=dose limiting toxicity; DOR=duration of objective response; IFN- γ =interferon-gamma; iRECIST=immune-related Response Evaluation Criteria in Solid Tumors; MTD=maximum tolerated dose; NCI=National Cancer Institute; ORR=objective response rate; OS=overall survival; PFS=progression-free survival; PK=pharmacokinetic; PR=partial response; RECIST=Response Evaluation Criteria in Solid Tumors; RP2D=recommended Phase 2 dose; SD=stable disease.

4. PATIENT SELECTION

Prospective approval of protocol deviations to recruitment and enrollment criteria, also known as protocol waivers or exemptions, is not permitted.

4.1 Inclusion Criteria

Patients must meet all the following criteria for study entry:

General Inclusion Criteria

1. Patients must have the ability to understand and the willingness to sign a written informed consent document.
2. Patients must be ≥ 18 years of age on day of signing informed consent document.

Because no dosing or AE data are currently available on the use of NT-I7 in patients < 18 years of age, children are excluded from this study.

3. Eastern Cooperative Oncology Group (ECOG) performance status ≤ 2 (Karnofsky $\geq 60\%$, see [Appendix A](#)). Exceptions, such as bilateral amputation for trauma, could be approved following consultation with the Protocol PI and/or ION Coordinating Center.
4. Patients must have a life expectancy of greater or equal to 12 weeks.
5. Patients must have adequate organ and marrow function as defined below:
 - Absolute neutrophil count $\geq 1,000/\text{mcL}$
 - Platelets $\geq 100,000/\text{mcL}$
 - Hemoglobin $\geq 8.0 \text{ g/dL}$
 - Total bilirubin $\leq 1.5 \times$ institutional upper limit of normal (ULN) (however, patients with known Gilbert’s disease who have serum bilirubin level $\leq 3 \times$ ULN may be enrolled.)
 - AST(SGOT)/ALT(SGPT) $\leq 3 \times$ ULN (AST and/or ALT $\leq 5 \times$ ULN for patients with liver involvement.)
 - Alkaline phosphatase $\leq 2.5 \times$ ULN ($\leq 5 \times$ ULN for patients with documented liver involvement or bone metastases.)
 - Creatinine clearance $\geq 30 \text{ mL/min/1.73 m}^2$ by Cockcroft-Gault:

$$\frac{(140 - \text{age}) \times (\text{weight in kg}) \times (0.85 \text{ if female})}{72 \times (\text{serum creatinine in mg/dL})}$$

At the discretion of the treating physician, a 24-hour urine creatinine clearance could be obtained and utilized as the gold standard if creatinine clearance by Cockcroft-Gault is < 30 , and prevents patient enrollment on the trial.
 - INR and aPTT $\leq 1.5 \times$ ULN (This applies only to patients who do not receive therapeutic anticoagulation; patients receiving therapeutic anticoagulation, such as low-molecular-weight heparin or warfarin, should be on a stable dose.)
6. Patients positive for HIV are allowed on study, but HIV-positive patients must have:
 - a. A stable regimen of highly active antiretroviral therapy (HAART)
 - b. No requirement for concurrent antibiotics or antifungal agents for the prevention of opportunistic infections
 - c. A CD4+ count above 100 cells/mcL and an undetectable HIV viral load on standard polymerase chain reaction (PCR)-based tests

7. Female patients of childbearing potential (including women who have had a tubal ligation) must have a negative serum pregnancy test within 72 hours prior to Cycle 1, Day 1 and must agree to remain abstinent (refrain from heterosexual intercourse) or use contraceptive methods that result in a failure rate of < 1% per year during the study treatment period and for at least 150 days after the last dose of study agent(s) – refer to Section [5.5](#) for further details.
8. Men must agree to remain abstinent (refrain from heterosexual intercourse) or use contraceptive methods that result in a failure rate of < 1% per year during the study treatment period and for at least 150 days after the last dose of study agent(s). Men must agree to refrain from donating sperm during this same period – refer to Section [5.5](#) for further details.

Cancer-Specific Inclusion Criteria

9. Patients must have histologically or cytological documented locally advanced/inoperable or metastatic skin cancer including melanoma, MCC and cSCC.

Note: Cancer must be invasive; carcinoma in situ is excluded.

Note: Patients must have cutaneous melanoma; mucosal melanoma is excluded.

10. **Arm I:** Anti-PD-1/PD-L1 naïve cSCC and MCC.

Arm II: Anti-PD-1/PD-L1 relapsed/refractory MCC, cSCC and melanoma.

Note: Each arm and each cancer type have different eligibility criteria (see below).

Arm I – cSCC: Patients must have biopsy-proven metastatic cSCC or locoregional cSCC that has recurred following standard locoregional therapy with surgery and/or radiation therapy.

Arm I – MCC: Patients must have biopsy-proven metastatic MCC or locoregional MCC in need of systemic therapy, including patients that have not had prior systemic therapy or have recurred following standard locoregional therapy with surgery and/or radiation therapy. Prior chemotherapy is allowed.

Note: For Arm II patients, eligibility will be determined by clinical progression or radiographic progression. Response Evaluation Criteria in Solid Tumors (RECIST) 1.1 will be used for patients on prior protocols that have mandated serial RECIST readings. In addition, the following criteria will be applied for each tumor types.

Arm II – MCC: Patients must have biopsy-proven metastatic MCC or locoregional MCC that has recurred following anti-PD-1 or anti-PD-L1, or has stable disease (SD) following anti-PD-1 or anti-PD-L1, defined as a minimum of 6 weeks of SD per RECIST 1.1 criteria. Patients may have also failed other systemic regimens, e.g., chemotherapy.

Note: Progression following investigational therapies is allowed.

Arm II – cSCC: Patients must have biopsy-proven metastatic cSCC or locoregional cSCC that has recurred following anti-PD-1 or anti-PD-L1, or has SD following anti-PD-1 or anti-PD-L1, defined as a minimum of 6 weeks of SD per RECIST 1.1 criteria.

Note: Progression following investigational therapies is allowed.

Arm II – melanoma: Patients must have biopsy-proven metastatic melanoma or locoregional melanoma that has recurred following anti-PD-1, anti-PD-L1, or has SD following anti-PD-1 or anti-PD-L1, defined as a minimum of 6 weeks of SD per RECIST 1.1 criteria.

Note: Prior therapy with ipilimumab is allowed (subject to a 6-week washout period) but not required.

Note: Progression following targeted therapies (e.g., BRAF inhibitor and/or MEK inhibitor) or other approved (e.g., talimogene laherparepvec [T-VEC]) or investigational therapies is allowed.

11. Patients must have measurable disease per clinical exam or per RECIST 1.1 assessed by computed tomography (CT) scan or magnetic resonance imaging (MRI). See [Section 11](#) for the evaluation of measurable disease.
12. Patients must have biopsiable disease (i.e., have at least 1 tumor lesion that is accessible and feasible to biopsy) as determined by the treating physician.
13. Patients must provide tissue from an archival tumor sample (obtained after last therapy) or newly obtained (preferred) core biopsy, punch biopsy, or surgical excision of a primary or metastatic tumor lesion.

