4.2 Exclusion Criteria

Patients who meet any of the following criteria will be excluded from study entry.

General Exclusion Criteria

1. Inability to comply with study and follow-up procedures.
2. Pregnancy, lactation, or breastfeeding.
3. Significant cardiovascular disease, such as New York Heart Association cardiac disease (Class II or greater), myocardial infarction (within the last 3 months), uncontrolled hypertension, unstable arrhythmia and/or unstable angina.
4. Poorly controlled Type 2 diabetes mellitus defined as a screening hemoglobin A1C $\geq 8\%$ or a fasting plasma glucose ≥ 160 mg/dL (or 8.8 mmol/L).

5. Major surgical procedure, other than for diagnosis, within 28 days prior to Cycle 1, Day 1, or anticipation of need for a major surgical procedure during the study.
6. Any other diseases, metabolic dysfunction, physical examination finding and/or clinical laboratory finding giving reasonable suspicion of a disease or condition that contraindicates the use of an investigational drug or that may affect the interpretation of the results or may render the patient at high risk from treatment complications.
7. Prisoners or subjects who are compulsorily detained (involuntarily incarcerated) for treatment of either a psychiatric or medical (e.g., infectious) illness.

Cancer-Specific Exclusion Criteria

8. Patients who have had chemotherapy or radiotherapy within 2 weeks (4 weeks for nitrosoureas or systemic mitomycin C) prior to Cycle 1, Day 1.
9. Patients who had prior treatment with immune CPIs, immunomodulatory monoclonal antibodies (mAbs), and/or mAb-derived therapies within 6 weeks before the initiation of study treatment, except for:
 - Prior anti-PD-L1/anti-PD-1 requires a 3-week washout period.
 - Prior anti-CTLA-4 requires a 6-week washout period.
10. Patients who have not recovered from AEs (other than alopecia, vitiligo, neuropathy or endocrinopathy managed with replacement therapy) due to agents administered more than 4 weeks earlier (i.e., have residual toxicities >Grade 1). However, the following therapies are allowed:
 - Hormone-replacement therapy or oral contraceptives
 - Herbal therapy ≥ 1 week before initiation of study treatment (herbal therapy intended as anticancer therapy must be discontinued at least 2 weeks before initiation of study treatment)
 - Palliative radiotherapy for bone metastases >2 weeks prior to Cycle 1, Day 1.

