Based on the available data provided in Section 2.2, the average historical ORR for the patients in this study would be 45.25% in Arm I and less than 5% in Arm II. With a total of 24 patients treated at the RP2D in Phase 2a of the study in Arm I, the 95% confidence interval for an observed ORR of 17/24 or higher would exclude 45.25%. With a total of 36 patients treated at the RP2D in Phase 2a of the study in Arm II, the 95% confidence interval for an observed ORR of 6/36 or higher would exclude 5%.

Approximately 84 patients will be enrolled in this study; up to approximately 24 patients in the Phase 1b and approximately 60 evaluable patients in the Phase 2a of the study. The expected accrual is 4 patients per month total at approximately 8 ION sites.

Safety Population: All patients who receive at least 1 dose of the investigational regimen will be considered evaluable for safety and included in the overall safety analysis. For the Phase 1b, in the absence of a DLT, patients must complete the full 3-week DLT window period to be considered evaluable for DLTs. Patients who discontinue from the study before the completion of the full 3-week (21 days) DLT window for reasons other than the occurrence of a DLT (e.g., withdrawal of consent, rapid tumor progression, death due to rapid tumor progression, AE that does not meet DLT criteria) will not be considered evaluable for DLTs and will be replaced.

Efficacy Population: The efficacy analysis for the Phase 1b (dose escalation) portion will be conducted on all DLT-evaluable patients, as defined in Section 6.2.2. The efficacy analysis for the Phase 2a (expansion phase) portion will be conducted on all patients who received at least one cycle of study treatment and have at least one evaluable post baseline tumor assessments.

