4.2.6. Subpopulations

No analyses of subpopulations of patients are planned.

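### Arm II entry rules conflict on whether stable disease suffices, yet the whole arm is compared with one historical ORR of under 5% that the cited section does not contain

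*Protocol*

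**What the plan says.** **Entry.** Protocol 4.1 labels the arm "Anti-PD-1/PD-L1 relapsed/refractory MCC, cSCC and melanoma". A note ahead of the tumor-specific criteria states: "For Arm II patients, eligibility will be determined by clinical progression or radiographic progression". It adds that the criteria for each tumor type apply as well. Those criteria offer a second route beside recurrence. For MCC the patient may qualify who "or has stable disease (SD) following anti-PD-1 or anti-PD-L1, defined as a minimum of 6 weeks of SD per RECIST 1.1 criteria"; for cSCC and melanoma the clause reads "or has SD following anti-PD-1 or anti-PD-L1, defined as a minimum of 6 weeks of SD per RECIST 1.1 criteria". Protocol 4.2, exclusion 9, adds "Prior anti-PD-L1/anti-PD-1 requires a 3-week washout period".

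**Benchmark.** Protocol 15.3, repeated in SAP 4.1, says that on the data in Protocol 2.2 "the average historical ORR for the patients in this study would be 45.25% in Arm I and less than 5% in Arm II". It then says that a 95% confidence interval from 6/36 or more responses in Arm II would exclude 5%. The interval method is not named.

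**Cited source.** The table in Protocol 2.2 lists checkpoint-inhibitor ORRs: cSCC 47%, MCC 33% to 56%, melanoma 33% to 40%. It has no entry for patients already treated with anti-PD-1/PD-L1.

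**Analysis.** ORR is the Phase 2a primary endpoint (Protocol 3, Table 2). Protocol 15.5.1 calls for separate analyses of each Phase 2a arm. SAP 4.2.1 instead pools efficacy by dose, with one group made of all 1200 µg/kg patients from both phases. SAP 4.2.6 states: "No analyses of subpopulations of patients are planned".

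**The concern.** In a single-arm comparison the benchmark carries the whole inference. Every Arm II patient receives atezolizumab and there is no atezolizumab-only control, so reading an excess over 5% as the contribution of NT-I7 requires 5% to be the rate these patients would show on atezolizumab alone.

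Two things weaken that. First, the figure describes a relapsed/refractory population, while the tumor-specific criteria, taken at face value, admit patients who have not progressed and who stopped a similar agent as little as three weeks earlier. Protocol 6.5 itself says that responses to immunotherapy can come later than with cytotoxic drugs. Second, the section cited for the figure does not contain it, so a reader cannot check which population it describes.

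At stake is the meaning of the only efficacy yardstick given for Arm II. If SD-entry patients make up a material part of the arm and respond more often than 5% without NT-I7, an interval lying above 5% could reflect the mix of patients. The planned summaries would not show this, because they separate neither the arms nor the entry routes.

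**Working it through.** **1. The plan's own figure.** Inputs from Protocol 15.3: n = 36, benchmark 5%, 95% interval. The exact (Clopper-Pearson) lower limit for r responses is the 2.5% quantile of a Beta(r, n − r + 1) distribution.

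- 5/36: lower limit 4.67%, so 5% is not excluded.
- 6/36: interval 6.37% to 32.81%, so 5% is excluded.

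The stated 6/36 is therefore reproduced. Wilson and Jeffreys intervals would already exclude 5% at 5/36 (lower limits 6.08% and 5.50%). A Wald interval would not exclude it at 6/36 (4.49%). The exact method is evidently the one used.

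If the true ORR is 5%, P(X ≥ 6) for X ~ Binomial(36, 0.05) is 0.83%.

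**2. Dependence on the benchmark.** The exact lower limits are 6.37% at 6/36, 8.19% at 7/36 and 10.12% at 8/36. So 6/36 excludes neither 8% nor 10%; these need 7/36 and 8/36. P(X ≥ 6) is 6.4% at a true ORR of 8% and 14.5% at 10%.

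**3. A mixed arm.** Let m patients enter with SD and respond at rate q without an NT-I7 effect, and let the other 36 − m respond at rate p. Then

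P(at least 6) = 1 − Σ (a = 0 to 5) P[Bin(m, q) = a] × P[Bin(36 − m, p) ≤ 5 − a].

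Neither m nor q is in the documents; both are assumptions. For p the plan says only under 5%, so 5% is the upper end and 3% is shown as an alternative (also an assumption).

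For m = 11, q = 20%, p = 5%, the six products are 0.0858 + 0.2345 + 0.2852 + 0.1933 + 0.0711 + 0.0108 = 0.8807, so the probability is 11.9%.

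| SD-entry patients (m) | Assumed ORR (q) | Pooled ORR, p = 5% | P(≥ 6/36), p = 5% | P(≥ 6/36), p = 3% |
|---|---|---|---|---|
| 7 | 10% | 6.0% | 1.8% | 0.4% |
| 11 | 20% | 9.6% | 11.9% | 6.2% |
| 18 | 30% | 17.5% | 63.2% | 56.9% |

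The pooled ORR is (m·q + (36 − m)·p)/36; for the middle row, (11 × 0.20 + 25 × 0.05)/36 = 3.45/36 = 9.6%.

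**4. Effect of a split.** If only progressed patients are compared with 5%, the minimum count follows their number. At n = 25, 4 responses give a lower limit of 4.5% and 5 give 6.8%, so 5 are needed. At n = 18, 4 responses suffice (6.4%).

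**The case against.** The strongest reply is that the note in Protocol 4.1 makes progression the deciding condition and applies the tumor-specific criteria on top of it. On that reading an SD patient must also have progressed, and 5% may fit the arm. This stands as far as it goes: a reader might infer that Arm II certainly admits patients with SD alone, and the documents do not settle that. But the reading leaves the SD alternative, written into all three cohorts, with little or no function. The passages conflict.

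Second, no passage gives a response rate for SD patients who continue PD-1/PD-L1 blockade, so the premise that they respond more often is an assumption. This stands. The 63% needs half the arm to enter with SD and respond at 30%, close to the 33% low end of the checkpoint-inhibitor rates in Protocol 2.2, although these patients have already had such an agent. With progressed patients at 3%, the middle case falls from 11.9% to 6.2%.

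Third, a reader might take 6/36 as a test or a success criterion. The documents do not support that: it says when an interval would exclude 5%, no decision is attached, and SAP 4.2.5 reports no p-values. Inability to attribute responses to NT-I7 is also inherent in the lack of a control and is not created by the SD clause.

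Fourth, SAP 5 records premature closure and few responses, so Arm II may not have reached 36. This stands. It limits the n = 36 probabilities and is a reason to work at the actual n.

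**Conclusion.** The point holds in conditional form. Three parts rest on the text alone: Protocol 4.1 contradicts itself on whether SD is enough for Arm II, the under-5% figure is credited to a section that does not contain it, and the SAP has no efficacy summary for Arm II, let alone by entry status.

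The numerical consequence is a sensitivity result. The 6/36 count is correct for 5%, with a 0.8% chance of occurring at that rate. With no NT-I7 effect the chance runs from about 2% to 63% over the three mixtures shown with progressed patients at 5%, and from 0.4% to 57% with them at 3%. At the low end the problem is negligible.

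It would go too far to conclude that 5% is the wrong benchmark, or that 6/36 would have been reached without NT-I7. The documents show only that the figure is unsourced and may describe a narrower group than the one enrolled. The correction is worth making because ORR is the Phase 2a primary endpoint and this is its only reference value in Arm II.

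**What to change.** 1. **Protocol 4.1.** Reconcile the Arm II note with the SD clauses in the MCC, cSCC and melanoma criteria, and state which reading was applied at enrollment.
2. **Protocol 15.3 and SAP 4.1.** Remove the attribution of the Arm II figure to Protocol 2.2. Give its actual source and population, or label it an assumption. Add that 6/36 does not exclude 8% or 10%, which need 7/36 and 8/36.
3. **SAP 4.2.1, 4.2.6 and 4.8.1.** Report Phase 2a ORR by arm, as Protocol 15.5.1 specifies for its analyses. SAP 4.2.1 has to change first, since pooling by dose leaves no Arm II table to divide. If SD-entry patients were enrolled, report Arm II ORR with exact 95% intervals separately for progressed and SD-entry patients, and compare only the progressed group with 5%, at its actual n.

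The cost is some added tables and a text correction, with no design change. The drawbacks are small denominators and wider intervals. Entry status may also have to be taken from eligibility or prior-therapy records, since nothing in the documents shows that it was a coded field. Classification may be uneven, because Protocol 4.1 accepts clinical progression and uses RECIST only for patients from earlier protocols that required it.
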